# 6.1.3. Dose modification for eye toxicity (Table 9).

For toxicities related to visual symptoms related to CB-103, refer to the following table. In general, it is suggested that the patient avoids sudden exposure to bright sun light allowing time for possible delayed light accommodation.

Table 9: Dose modifications for ocular/vision related toxicities

Dose Modifications for CB-103							
Worst Toxicity CTCAE Grade unless otherwise specified (Value)	At any time during a cycle of CB-103 (including intended day of dosing)						
Visual symptoms							
Grade 1	Maintain dose level						
Grade 2	Omit dose administration until resolved to ≤ Grade 1 (or baseline), then continue treatment with CB-103 at the current dose level						
	If visual symptoms ≥ Grade 2 recur upon re-exposure to CB-103 and if is intolerable by patient, discontinue patient from study						
Grade 3	Omit dose administration and discontinue patient from study						
Grade 4	Omit dose administration and discontinue patient from study						

Grading according to NCI-CTCAE v.5.0 guideline.

# 6.1.4. Dose modification for gastro-intestinal toxicities (diarrhoea) (Tables 10-11)

In non-clinical studies in different species (dog, rat, mouse), CB-103 administered at different doses and administration schedules did not show any gastro-intestinal toxicities, e.g. diarrhoea, weight loss. However, as other Notch inhibitors (GSIs, mABs) have shown diarrhoea as their major DLT, there might be a risk for CB-103 to also develop gastro-intestinal toxicities. In the event that diarrhoea is observed in clinical trial patients, the following algorithm for CB-103 dose modifications should be followed. Furthermore, section **6.1.7.** provides a management plan for the occurrence of diarrhoea with a description of measures and treatment suggestions.

Table 10: NCI CTCAE version 5.0 grading of diarrhoea

Grading	0	1	2	3	4	5
Diarrhoea	None	stools per day over baseline; mild increase in ostomy output	per day over baseline; moderate increase in ostomy output compared to baseline: limiting instrumental	severe increase in ostomy output compared to		Death

**Definition:** A disorder characterized by an increase in frequency and/or loose or watery bowel movements.

Page | 22 04/25/2024

Table 11: CB-103 Dose Modifications for Gastro-Intestinal Toxicity

Dose Modifications of CB-103 for Gastro-Intestinal Toxicity							
Worst Toxicity CTCAE Grade unless otherwise specified (Value)	At any time during a cycle of CB-103 (including intended day of dosing)						
Grade 1	Maintain dose level						
Grade 2 (see section 6.1.7. for treatment algorithm)	Omit dose administration until recovery to Grade 0 or baseline then continue at current dose level if grade 2 toxicity persisted for ≤ than 7 days.  If grade 2 toxicity persisted for more than 7 days decrease dose by 1 dose level after resolution to Grade 0 or baseline						
Grade 3 (see section 6.1.7. for treatment algorithm)	Omit dose administration until recovery to Grade 0 or baseline then decrease the next scheduled dose by 1 dose level						
Grade 4 (see section 6.1.7. for treatment algorithm)	Omit dose administration until recovery to Grade 0 or baseline then decrease the next scheduled dose by 1 dose level*  In the event Grade 4 toxicity lasts > 24 hours despite maximal medical attention discontinue treatment.  If grade 4 toxicity lasts < 24 hours reduce dose by 1 dose level at next cycle If toxicity recurs discontinue treatment.						
All grades	At the first sign of abdominal cramping, loose stools, or onset of diarrhoea, the patient should be treated according to section 6.1.7 . according to the recommended treatment algorithm.  Omit dose administration of CB-103 for ≥ CTCAE grade 2 diarrhoea only if diarrhoea could not be controlled despite the use of optimal anti-diarrhoea treatments.						

Grading according to NCI-CTCAE v.5.0 guideline.

# 6.1.5. Dose modification for cardiac toxicity (Table 12)

As in non-clinical studies with CB-103, QT prolongation was observed at higher doses and ECG changes in patients may be observed, therefore, intensive cardiac monitoring is implemented into this study with central management and review of multiple ECGs and Holter ECGs at selected timepoints. Furthermore ECHO/MUGA scans and cardiac markers will be assessed at selected time points. For toxicities related to QTc prolongation, refer to the table below.

The study treatment should be halted for any patient who experiences grade 4 QT prolongation (torsades or other related event) unless a clear alternative cause for the event can be identified and the event completely reverses with correction of the underlying issue.

Table 12: Dose modifications for cardiac abnormalities

Dose Modifications for CB-103					
Worst Toxicity CTCAE Grade unless otherwise specified (Value)	At any time during a cycle of CB-103 (including intended day of dosing)				
Cardiac - Prolonged QTcF interval 					
During Cycle 1:					
Absolute QTcF< 450 ms	Maintain dose level and ECG monitoring as per visit schedule.				
QTcF ≥ 450 ms and < 480 ms	Maintain dose level. ECG monitoring assessments should be increased as indicated (e.g. hourly until no QTcF ≥ 450 ms). Consider discontinuation of concomitant QT prolonging agents.				
During any Cycle:					
Grade 3 or QTcF ≥ 480 ms as identified by the Investigator on the ECG.	Omit dose administration and recommend discontinuation of concomitant QT prolonging agents. Monitor patient with frequent ECGs as indicated (e.g. hourly) until the QTcF has returned to ≤ 450 ms. Further monitoring as clinically indicated. Exclude other causes of QTc prolongation such has hypokalaemia, hypo-magnesaemia and blood oxygenation status. Once QTcF prolongation has resolved, and if the QTcF prolongation was confirmed by central reading, patients may be re-treated at one lower dose level at the Investigator's discretion.  ECG monitoring must continue throughout the treatment				
	
 
period as follows:
 
ECG monitoring assessments should be performed for 2 additional cycles at higher frequency as clinically indicated
 
If the ECGs obtained in the first additional cycle after dose reduction are without any QTcF prolongation, then ECG monitoring in subsequent cycles will be continued as per the visit schedule.
 
If the patient had an absolute QTcF ≥ 450 ms and < 480 ms, then ECG monitoring at a higher frequency will be continued for all subsequent cycles.
 
Patients who experience absolute QTcF ≥ 480 ms after one dose reduction will be discontinued from study.
 
				

Abbreviations: AE, adverse event; QTcF, corrected QT interval using Fridericia formula. Grading according to NCI-CTCAE v.5.0 guideline.

Exclude other causes of QTcF prolongation such has hypokalemia, hypomagnesemia and blood oxygenation status. Patients who develop hypokalemia or hypomagnesemia during the study should receive electrolyte replacement as soon as possible and should not receive further CB-103 dosing until the respective electrolytes are documented to be within normal limits.

Page | 24 04/25/2024

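### Section 6.1.5 halts treatment for grade 4 QT prolongation, but Table 12 leaves the same patient open to re-treatment; its ECG bullets also leave the monitoring period unclear

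*Combined protocol and SAP*

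**What the plan says.** Section 6.1.5 of the combined protocol and SAP deals with QT events in two places.

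**Text above Table 12.** "The study treatment should be halted for any patient who experiences grade 4 QT prolongation (torsades or other related event"; the sentence then makes an exception where a definite other cause is found and the event resolves completely once that cause is corrected. The preceding paragraph sends the reader to Table 12 for QTc toxicities.

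**Table 12.** No row is labelled grade 4. The most severe row covers grade 3 events or any QTcF of 480 ms and above. CB-103 is omitted, other causes are to be excluded, and once the prolongation has resolved, if central reading confirmed it, "patients may be re-treated at one lower dose level at the Investigator's discretion". The footnote also bars CB-103 until low potassium or magnesium is corrected.

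The same row then sets ECG monitoring in four bullets:

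1. "ECG monitoring assessments should be performed for 2 additional cycles at higher frequency as clinically indicated".
2. Where the first such cycle shows no prolongation, "then ECG monitoring in subsequent cycles will be continued as per the visit schedule".
3. For QTcF from 450 to below 480 ms, "then ECG monitoring at a higher frequency will be continued for all subsequent cycles".
4. For a repeat event: "Patients who experience absolute QTcF ≥ 480 ms after one dose reduction will be discontinued from study".

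**The concern.** The main issue is resumption of CB-103 after a grade 4 QT event. The text makes it conditional on finding and correcting another cause. The table row makes it a matter of investigator discretion after resolution and central confirmation. Two investigators who each follow section 6.1.5 could act differently on the same patient.

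The lesser issue is how long a re-treated patient is watched closely. The first bullet says two cycles, and the second ends the closer monitoring after one. Later cycles matter because section 4.2.3 lets patients in CR or CRi continue until progression or transplant. Section 7.2 also makes its restrictions on QT-prolonging drugs depend on what the scheduled ECGs show.

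The section justifies its cardiac monitoring by QT prolongation seen at higher doses in non-clinical studies, so these instructions should be unambiguous. At stake is the handling of a few individual patients after a serious cardiac signal.

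**Working it through.** No figure in the plan needs reproducing. The check sets the passages side by side.

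**Step 1. Grade 4 events**

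| | Text of 6.1.5 | Table 12, most severe row |
|---|---|---|
| Who is covered | Grade 4 QT prolongation, torsades or related event | Grade 3, or any QTcF of 480 ms or more |
| Upper limit or grade 4 exclusion | Not applicable | None |
| First action | Halt study treatment | Omit CB-103 |
| Condition for resuming | Another clear cause found, and full reversal on correcting it | Resolution and central confirmation; other causes to be excluded |
| Must another cause be found? | Yes | No |

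The two limbs of the row are joined by *or*, so a grade 4 event with QTcF of 480 ms or more meets the second limb. There are then two cases:

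- Another cause is found and the event reverses: both places allow treatment to resume, so they need not conflict.
- No other cause is found: the text halts treatment, and the row permits CB-103 at one lower dose level.

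The conflict is confined to the second case. Neither place says which governs. The other CB-103 modification tables do place grade 4: Table 7 (creatinine), Table 8 (bilirubin, AST/ALT), Table 9 (visual), Table 11 (gastro-intestinal) and Table 13 (non-laboratory).

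**Step 2. ECG monitoring after re-treatment**

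A cycle is 28 days (section 4.1), so one cycle is 1 × 28 = 28 days and two are 2 × 28 = 56 days. Assume that prolongation means QTcF of 450 ms or more, as the table's cut-points suggest, and that bullet 3 applies in whichever cycle the value occurs.

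| First additional cycle | Bullet 1 | Later bullets |
|---|---|---|
| Below 450 ms | 2 cycles (56 days) | Bullet 2: 1 cycle (28 days), then visit schedule |
| 450 to below 480 ms | 2 cycles | Bullet 3: all later cycles |
| 480 ms or more | – | Bullet 4: discontinued |

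Under these assumptions the two-cycle period decides no case. For the clean patient, the second cycle has either intensified ECGs or the routine schedule, which after cycle 1 is an ECG on Day 1 of the cycle (section 8.7.1, Table 16).

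**Step 3. Sensitivity to the assumptions**

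Bullet 2 does not define prolongation. If it also covered a rise from baseline to a value still below 450 ms, that patient would meet neither bullet 2 nor bullet 3, and the two cycles of bullet 1 would apply. If instead the threshold were higher for some patients (the screening limit in 3.2.5.7 is 450 ms for males and 470 ms for females), a female patient at 460 ms would count as clean under bullet 2 but stay on intensified monitoring under bullet 3. The result depends on a threshold that the table does not state.

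**The case against.** **Grade 4.** The best defence is that text and table complement each other: the text handles grade 4 and the row names grade 3. The row is also only permissive, so an investigator who halts treatment complies with both. That much stands: nobody is forced to breach either sentence. But the row's second limb is open-ended and precedence is not stated, so an investigator working from the table is given a permission that the text withholds.

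The row has safeguards: other causes excluded, central confirmation, resolution, and corrected electrolytes under the footnote. These are real, but none requires that another cause be found. Table 13 discontinues patients for grade 4 non-laboratory events, and section 4.3.3 ends treatment for unacceptable events. Table 13, however, is headed as applying after cycle 1 and does not say whether it covers QT events; if it does, it is a further instruction to reconcile with Table 12.

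**ECG bullets.** A reader might infer that the bullets flatly contradict each other and that no path can give two cycles. The documents do not support that. Bullet 2 is conditional and refers back to the first additional cycle, so it can be read as an early step-down from a two-cycle default. Bullets 3 and 4 name no cycle, the meaning of prolongation is undefined, and bullet 1 is qualified by clinical indication. What remains is that the table never calls the two cycles a default, and on its own cut-points the figure has no case to govern.

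**Conclusion.** The grade 4 conflict holds as written, for one defined case: a grade 4 QT event with QTcF of 480 ms or more and no other clear cause. The text halts treatment; the table allows re-treatment at discretion. It rests on reading the second limb of the row literally and on the absence of any precedence rule.

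The ECG point is secondary. It is an unclear monitoring period (28 v 56 days after a clean first cycle) and an undefined threshold, not a proven contradiction.

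Few patients should be affected. No QTc prolongation was reported in the 79-patient first-in-human study (section 2.3.2), and up to 30 patients are planned here (section 12). A reader might infer that the trial's QT safety as a whole, or its primary results, turn on this. They do not: the ORR endpoint, the stopping boundaries in Table 18 and the sample size are unaffected. The point merits correction because each such event is serious and the remedy is wording.

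**What to change.** Reconcile the passages within section 6.1.5:

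- Make Table 12 and the text give the same action for grade 4 QT events. Either add a grade 4 row, or exclude grade 4 explicitly from the row for QTcF of 480 ms and above and cross-refer to the text.
- Make bullets 1 to 3 agree on the period of intensified ECGs after a clean first cycle. If a step-down is meant, say so.
- State the QTcF value that counts as prolongation in bullet 2.

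Which action and which monitoring period apply is the sponsor's clinical decision; this review takes no position on it. The cost is a wording amendment to one section, and neither monitoring period already written in the table would need a new procedure.

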# 6.1.6. Dose modification for non-laboratory toxicities (Table 13)

Patients who experience non-laboratory DLTs must be evaluated at least once a week following demonstration of the toxicity until resolution of the toxicity to allow for retreatment, stabilisation of the toxicity, or study treatment completion.

Table 13: Dose modification for non-laboratory toxicities

Dose Modifications for CB-103 post cycle 1							
Worst Toxicity CTCAE Grade unless otherwise specified (Value)	At any time during a cycle of CB-103 (including intended day of dosing)						
Non-laboratory AEs							
Grade 1 or 2	Maintain dose level						
Grade 3	Omit dose administration until resolved to ≤ Grade 1, then ↓ 1 dose level						
Grade 4	Omit dose administration and discontinue patient from study						

Grading according to NCI-CTCAE v.5.0 guideline.

# 6.1.7. Diarrhoea and Nausea Management Plan

Although no signs of gastro-intestinal toxicities (e.g., diarrhoea) were observed in the nonclinical safety and toxicology studies in different species (dog, rat, mouse) treated with CB-103 at different doses and administration schedules, the occurrence of diarrhoea cannot be excluded.

## 6.1.7.1. General measures:

- Stop all lactose-containing products, alcohol
- Stop laxatives, bulk fibre (e.g., Metamucil\*, Procter & Gamble), and stool softeners (docusate sodium; Colace, Roberts)
- Drink 8 to 10 large glasses of clear liquids per day (e.g., water, Pedialyte® (Ross), Gatorade (Quaker), broth)
- Eat frequent small meals (e.g., bananas, rice, apple sauce, Ensure®, toast)
- Stop high-osmolar food supplements such as Ensure Plus and Jevity Plus (with fibre)

It is recommended that patients be provided loperamide tablets. It is mandatory that patients are instructed on the use of loperamide at cycle 1 in order to manage signs or symptoms of diarrhoea at home. Patients should be instructed to start oral loperamide (initial administration of 4 mg, then 2 mg every 4 hours (maximum of 16 mg/day) at the first sign of loose stool or symptoms of abdominal pain. These instructions should be provided at each cycle and the investigational site should ensure that the patient understood the instruction. At the beginning of each cycle, each patient should be specifically questioned regarding any experience of diarrhoea or diarrhoea related symptoms. If symptoms were experienced, then the investigational site should question the patient regarding the actions taken for these symptoms.

Page | 25 04/25/2024

#### 6.1.7.2. Treatment of Diarrhoea Grade 1 or 2

Diarrhoea grade 1 or 2 will be treated with standard loperamide (initially at first administration 4 mg, then 2 mg every 4 hours [maximum of 16 mg/day] or after each unformed stool).

#### 12-24 hours later:

# Diarrhea resolved

- Continue instructions for dietary modification
- Gradually add solid foods to diet
- Discontinue loperamide after 12-hours diarrhoea-free interval

# Diarrhea unresolved

Persisting diarrhoea grade 1 or 2 will be treated with addition of opium tincture, dihydrocodeine tartrate tablets/injections and start early on with corticosteroids which is the recommended treatment for the development of goblet cell metaplasia seen with other Notch inhibitors. Treatment should be accompanied by monitoring the patient's condition (to rule out dehydration, sepsis, ileus), medical check and selected workup. Observe patient for response to antidiarrheal treatment and may also consider treatment with high dose corticosteroids.

Persisting diarrhoea grade 3 or 4 may be treated with high dose loperamide (initially 4 mg, then 2 mg every 2 hours), addition of opium tincture or dihydrocodeine tartrate tablets/injections and with high dose corticosteroids to potentially inhibit the development of the goblet cell metaplasia seen with other Notch inhibitors. Furthermore, start of i.v. fluids, parenteral nutrition and antibiotics as needed with monitoring of patients' condition (to rule out dehydration, sepsis, ileus), medical check and workup (perform appropriate additional testing) should be started immediately. Observe patient for response.

# After 12-24 hours:

# Diarrhoea resolved

- Continue instructions for dietary modification
- Gradually add solid foods to diet
- Discontinue loperamide and/or other treatment after 12-hours diarrhoea-free interval

# Diarrhoea unresolved

- If diarrhoea still persisting (NCI CTC grades 1 and 2), after 2 x 24 hours with high dose loperamide, opiates and corticosteroids then admit to hospital and employ measures as for grade 3 and 4 until diarrhoea resolved.
- If diarrhoea still persisting and progressed to NCI grades 3 and 4, employ measures described below.

# 6.1.7.3. Treatment of Diarrhoea Grade 3 or 4

Severe diarrhoea grade 3 or 4 may be treated with hospitalisation, high dose loperamide (initially 4 mg, then 2 mg every 2 hours, addition of opium tincture or dihydrocodeine tartrate tablets/injections as well as early start of administration of corticosteroids as being the recommended treatment for goblet cell metaplasia

Page | 26 04/25/2024

observed in patients treated with other Notch inhibitors. Furthermore, start of i.v. fluids, parenteral nutrition and antibiotics as needed with monitoring of patients' condition (to rule out dehydration, sepsis, ileus), medical check and workup. Observe patient for response.

# After 12-24 hours:

- If diarrhoea persisting administer high dose corticosteroids and consider subcutaneous (s.c.) Sandostatin/octreotide (100-500 μg three times daily [TID])
- Continue i.v. fluids, parenteral nutrition and antibiotics as needed
- If diarrhoea grade 3 or 4 still persists patients should receive besides corticosteroids opium tincture or dihydrocodeine tartrate injections s.c. or intramuscular (i.m.)
- If diarrhoea grade 3 or 4 is still persisting s.c. Sandostatin/octreotide (500-1000 µg TID) should be administered.
- To control and/or resolve diarrhoea, next cycle of treatment should be delayed by 1 or 2 weeks. Treatment should be continued only when diarrhoea resolved.

# 6.1.7.4. Diarrhea Workup

Perform appropriate tests (American Gastroenterological Association [AGA] Technical Review on the Evaluation and Management of Chronic Diarrhoea; Fine and Schiller, 1999).

# Spot stool analysis

- Collect stool separating it from urine (special containers, analysis immediately, exceptionally freeze samples)
- Blood
- Faecal leukocytes (Wright's staining and microscopy) or
- C. difficile toxin
- Faecal cultures such as Shigella and pathogenic E. coli enterotoxigenic, enterohaemorrhagic etc., possibly Aeromonas, Pleisiomonas (if suspected exposure to contaminated water)

Page | 27 04/25/2024

#### 6.2. Recommended Venetoclax Dose Modification.

Interrupt dosing, reduce number of days, or reduce dose for toxicities. Treatment modifications for venetoclax related toxicities will be performed as per the respective summaries of product characteristics (SmPC). As CB-103 and venetoclax do not have overlapping toxicity, dose modification of CB-103 is independent of venetoclax dose modification: treatment modifications for CB-103 related are described in **Section 6.1.** 

See the following **Tables 14a and 14b** for dose modifications for hematologic and other toxicities related to **venetoclax**. For patients who have had a dosing interruption greater than 1 week reassess for risk of TLS to determine if reinitiation with a reduced dose is necessary.

Table 14a: Recommended Dose Modifications of Venetoclax for Toxicitiesa

Event	Occurence	Action
	•	Tumor Lysis Syndrome
Blood chemistry		Withhold the next day's dose. If resolved within 24 to 48 hours of last dose, resume at the same dose.
changes or symptoms	Any	For any blood chemistry changes requiring more than 48 hours to resolve, resume at a reduced dose.
suggestive of TLS		For any events of clinical TLS b , resume at a reduced dose following resolution.
		Non-Hematologic Toxicities
Grade 3 or 4 non-		Interrupt venetoclax. Once the toxicity has resolved to Grade 1 or baseline level, VENCLEXTA therapy may be resumed at the same dose. No dose modification is required. Consider decreasing treatment days.
hematologic toxicities	2nd and subsequent occurrences	Interrupt venetoclax. Follow dose reduction guidelines in Table 14b when resuming treatment with Venetoclax after resolution. Consider decreasing treatment days. A larger dose reduction may occur at the discretion of the physician.
		Hematologic Toxicities
Grade 3 or 4 neutropenia with infection or fever; or	1st occurrence	Interrupt venetoclax. To reduce the infection risks associated with neutropenia, granulocyte-colony stimulating factor (G-CSF) may be administered with Venetoclax if clinically indicated. Once the toxicity has resolved to Grade 1 or baseline level, Venetoclax therapy may be resumed at the same dose. Consider decreasing treatment days.
Grade 4 hematologic toxicities (except lymphopenia)	occurrences	Interrupt venetoclax. Consider using G-CSF as clinically indicated. Follow dose reduction guidelines in Table 14b when resuming treatment with Venetoclax after resolution. Consider decreasing treatment days. A larger dose reduction may occur at the discretion of the physician.

Consider decreasing treatment days for those patients with toxicities. Treatment could be decreased from 28 days to 21, 14 or 7 days, depending on the PI. Discontinue venetoclax for patients who require dose reductions to less than 25% of the scheduled dose for more than 2 weeks.

aAdverse reactions were graded using NCI-CTCAE v.5.0 guideline.

bClinical TLS was defined as laboratory TLS with clinical consequences such as acute renal failure, cardiac arrhythmias, or sudden death and/or seizures.

Protocol 2021-0547 4/25/2024

**Table 14b:** Dose reduction for toxicity during Venetoclax treatment

Dose at Interruption, mg	Restart Dose, mg a
400	300
300	200
200	100
100	50
50	20
20	10

<sup>aDuring the ramp-up phase, continue the reduced dose for 1 week before increasing the dose.

